Scientific Advisory Board

- [name]. [name]
Full Professor of Obstetrics and Gynecology
Department of Women`s and Children`s Health, University of Liverpool, UK
[contact]

Sanitary device: The Arabin cervical pessary, which is CE-certified for preventing SPB (CE 0482 / EN ISO 13485: 2012 + AC:2012 annex III of the council directive 93/42 EEC).

Main objective: To assess the impact of placing a cervical pessary in twin pregnancies with cervical shortening on children`s survival without neurodevelopmental disability at the age of 3.

Study design: Prospective Open-label Multicentre International Collaborative Randomized Controlled Trial, in parallel groups, based on intention to treat comparing the placement of a cervical pessary with usual management in cases of twin pregnancies with cervical shortening

Main outcome: Children`s survival without neurodevelopmental disability at the age of 3 years.

Study population: Women attending the reference hospital due to a dichorionic twin pregnancy with cervical shortening \leq 25th percentile and fulfil the inclusion criteria the study will be proposed. The patients will be informed of the intended therapeutic effect and possible side effects. If they agree and after obtaining their informed consent, they will be randomised according to the respective gestational week to either usual management (=control group) or cervical pessary placement up to 37+0 weeks (= pessary group). According to the gestational week and when the cervical shortening lies under the 25th percentile the patients are randomized to the following subgroups: gestational age in weeks 16-20, gestational age in weeks 20-24 and gestational age in weeks 24-28.

Sample size:

A stratified design, which divides the sample among 3 strata according to week of gestation, is analysed using the two-sided, Chochran-Mantel-Haenzel test with a significance level of $\alpha=5\%$. Sample sizes, summed across all strata, of 250 in group 1 (pessary group) and 250 group 2 (control-group), overall 500, achieve 80% power to prove significant difference when the odds ratio is actually 2,29 corresponding to the lower limit of a one-sided 90% confidence interval of the results in van't Hooft (ProTwin Trial)¹².

To account for a drop out rate of 25%, overall n=672 pregnant women will be recruited.

Study calendar:

Starting recruitment: July 1st, 2018

Finishing recruitment and follow-up: Dec 31st, 2023

Final report: July 2024.

Table of contents

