 - Preterm birth before 30 weeks: rate of delivery before 29+6 weeks
 - Preterm birth before 28 weeks: rate of delivery before 27+6 weeks
 - Birth weight: median weight (g) of the newborns at birth
 - Fetal or neonatal death: rate of intrauterine demise or neonatal death during the first 24 hours
 - Neonatal morbidity: rate of major adverse neonatal outcomes before discharge from the hospital
 - Intraventricular Haemorrhage (IVH): grades III-IV
 - Retinopathy of prematurity
 - Respiratory Distress Syndrome (RDS): grades II-IV,
 - Need for ventilation > 72 h
 - Necrotising enterocolitis
 - Proven or suspected sepsis, antibiotics (>5 days)
 - Need (Duration in days) for neonatal special care (NICU)
 - Harm from intervention
- Mother:
 - Maternal death
 - Significant maternal adverse events (rate):
 - Heavy bleeding: bleeding that requires a medical intervention
 - Cervical tear: cervical rupture due to the pessary placement
 - Uterine rupture: rupture of the uterus due to contractions or surgery
 - Physical or psychological intolerance to pessary: discomfort or pain due to the pessary that makes daily life uncomfortable (number of cases)
 - Rupture of membranes before 32 weeks: rate of–rupture of amniotic membranes before 31+6 weeks

[figure not shown]
- Infection/inflammation
- Hospitalisation for threatened preterm labour before 32 weeks: requirement of hospitalisation due to preterm contractions that need medical treatment to try to stop them before 31+6 weeks (rate)
 - Mean hospital stay duration: number of days of admittance at the hospital
 - Use of tocolytic treatment: Type of tocolytic, days of treatment, dose

4.2. Description of the trial design.

Open Multicentre International Collaborative Randomized Controlled Trial, in parallel groups, based on intention-to-treat analysis comparing the placement of a prophylactic cervical pessary with usual management in twin pregnancies with shortened cervix ≤ 25 percentile

4.3. Flowchart.

4.4. Description of the medical device and the treatment regimen.

The cervical pessary is a vaginal device (silicone ring) that is used to treat pregnant women for preventing spontaneous preterm birth. This device can be easily placed around the uterine cervix without pain (see annex I).

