This database will be supervised and coordinated by PD [name], Bürgerhospital Frankfurt/M. (Webmaster).

4.8. Identification of data to be collected in the case report files (CRF) that should be considered as data source.

Data will be collected in E-CRF, provided by >[name] Wissenschaft, Berlin< on study software "Castor".

4.9. Definition of what is considered to be the end of the study.

The study will be finished after the 3 year-follow up examination concerning neurodevelopmental disabilities, which will be conducted on the surviving children of the participating patients.

5. Selection and withdrawal of subjects

5.1. Inclusion criteria.

- Dichorionic diamnionic twin pregnancy with
- 16-28 weeks of gestation
- Minimal age of 18 years
- Informed consent signature

5.2. Exclusion criteria.

- Monochorionic twin pregnancy
- Major fetal abnormalities (requiring surgery or leading to infant death or severe handicap)
- Cerclage prior to randomisation
- Uterine malformation
- Placenta previa totalis
- Active vaginal bleeding at the moment of randomization
- Spontaneous rupture of membranes at the time of randomization
- Silicone allergy

- Current participation in other RCT
- Painful regular uterine contractions

5.3. Withdrawal criteria.

If a participant may voluntarily withdraw from treatment or if it is necessary to remove the pessary due to the conditions described before, the patients will be followed as usual until delivery (intention-to-treat analysis).

The death of one twin is not an exclusion criterion for the pessary placement.

The replacement of patients is not applicable in this trial.

5.4. Rescue treatment criteria.

If the cervical length decreases later on during the pregnancy, the management of the pregnancy in each centre will be the usual.

In case of secondary cervical shortening in the follow-up period pessary treatment may be offered as a rescue treatment up to 32+0 weeks of gestation.

Cervical cerclage or progesterone are generally not indicated in twin pregnancies.

6. Treatment of Subjects

6.1. Treatments to be administered.

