A medically qualified investigator will assess the relationship of AEs to the study medication.

All SAEs must be reported to the main investigator. He will perform an initial check of the report, request any additional information, and he will notify it to the Ethics Committee. All SAE information will be recorded. It may be appropriate that some SAEs do not require immediate reporting but this must be justified. Justification might be determined, for example, by admission to hospital, or prolongation of hospitalization, where this is to be expected in the underlying disease or condition.

All adverse events (AE) life-threatening or resulting in death will be notified within 24 hours. All AE that are not life-threatening will be notified within 15 days. The rest of AE will be recorded and analyzed at the end of the study.

9. Statistics

9.1. Description of statistical methods.

The primary statistical aim is to compare the primary combined outcome “long-term survival without neuro-developmental disability at 3 years follow up” with a two-sided Cochran-Mantel-Haenszel-Test and a significance level of $\alpha=0.05$. The primary outcome refers to a combined event in any of the twin and will be analysed for all pregnancies with available primary endpoint. The stratified study design is accounted by this stratified test according to the gestation groups.

The main statistical evaluation will be performed at two time points. (1) The complete data set for the secondary endpoints will be available after the last women enrolled in this study has delivered her twins, so the analysis of these outcome parameter will be done right after this event. (2) The primary outcome will be evaluated 3 years after the last woman enrolled in this study has delivered her twins.

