A descriptive analysis by preterm birth will be carried out calculating means and medians for quantitative variables and proportions with 95% confidence intervals for categorical variables. In general, statistical comparisons with the pessary arm and the control arms or other group comparisons for primary and secondary outcomes will be performed with stratified tests as well as comparisons in the gestation subgroups. Events will be analysed for each twin and for single children assuming appropriate random effect regression models. Further subgroup analyses regarding the cervical length will be performed (e.g. CL 15 to 25mm and below 15mm). All tests, see also examples in the synopsis, will be two-sided using a significance level of $\alpha=0.05$.

For the primary endpoint we expect to have a drop out rate of up to 25% due to the long follow-up time (3 years) of the study; but we do not expect to have lost data for the secondary endpoints because for these parameters the study has a short follow-up time till time to birth only.

An interim analysis shall be conducted on key safety parameters after birth of 300 twins: the following safety endpoints will be assessed by a one-sided test with $\alpha=1\%$

- on level of the neonates: rate of preterm birth, time to birth, birth weight, death, neonatal morbidity, harm of intervention
- and on the maternal level: rate of hospitalisation for threatened preterm labour < 32 weeks, rate of PRoM <32 weeks, rate of infection / inflammation, rate of physical or psychological intolerance to pessary, rate of SAR/SAE, death.

The trial will be terminated as negative if a disadvantage for the pessary-treatment can be found in one of these tests. To guarantee a high safety level the significance level is chosen more conservatively than in a Bonferroni correction.

All analysis will be carried out with SPSS® version 19.0 or later (IBM Company SPSS Inc. Headquarters, Chicago, Illinois, USA) and R version 3.2.3 or later (R Foundation for Statistical Computing, Vienna, Austria).

Primary Outcome	Statistical Test
Children`s Long-Term Survival without Neuro-developmental Disability (3-Years-follow up)	Cochran-Mantel-Haenszel-Test, using 3 strata according to WoG
Secondary Outcome	Statistical Test
Birth before 34 Weeks of Gestation	Cochran-Mantel-Haenszel-Test, Chi-Quadrat Test
Time to Birth	Cox-Regression
Birthweight	van Elteren Test, Wilcoxon-Mann-Whitney Test
Fetal / Neonatal Death	Cochran-Mantel-Haenszel-Test, Chi-Quadrat Test

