Neonatal Morbidity	Cochran-Mantel-Haenszel-Test, Chi-Quadrat Test
Need for Hospitalization (mother)	Cochran-Mantel-Haenszel-Test, Chi-Quadrat Test
Days of Hospitalization (mother)	van Elteren Test, Wilcoxon-Mann-Whitney Test
Maternal Adverse Events	Cochran-Mantel-Haenszel-Test, Chi-Quadrat Test
Pessary Intolerance	Cochran-Mantel-Haenszel-Test, Chi-Quadrat Test
Vaginal Infections	Cochran-Mantel-Haenszel-Test, Chi-Quadrat Test

9.2. Expected number of subjects to be included.

For sample size calculation, we account for the stratified design and assume three equally large gestation groups. For the pessary group, we assume a combined event rate of at least 8% for the primary outcome and for the comparison of the pessary group with the control group we assume an odds ratio of 2.29. This odds ratio correspond to the lower bound of a one-sided confidence interval for the event rate given in van't Hooft (ProTwin Trial¹²). To reach a power of at least 80%, we have to evaluate at least 500 patients, 250 in the pessary group and 250 in the control group. To account for a drop out rate of 25%, overall n=672 pregnant women will be recruited.

9.3. Criteria for termination of the trial.

A non-justified case of maternal death (temporary stop until complete evaluation of the case by an external committee).

9.4. Selection of subjects to be included in each analysis.

The analysis will include all the subjects that have been randomised.

10. Direct Access to Data Source

Direct access will be granted to the authorized monitor, host institution and the regulatory authorities to permit trial-related monitoring, audits and inspections.

11. Quality and Control Assurance

Main investigator and collaborators: In order to ensure the Quality of the data they will provide instructions and training to the sites involved in the trial; review the CRF data; and detail of any other steps taken to ensure quality of research.

The main investigator will sign the study protocol and the “investigator’s commitment; he will apply for the Ethics Committee and the Director’s approval; and he will review the final report of the study.

The collaborators will assess patient’s eligibility, they will inform the patients and ask for the informed consent; and they will be responsible of the CRF and obtaining and registering all data.

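### The primary test uses only pregnancies with a known 3-year endpoint, and no missing-data or sensitivity analysis is planned for an expected loss of up to 25%

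*Combined protocol and SAP*

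**What the plan says.** Section 9.1 sets the population for the primary Cochran-Mantel-Haenszel (CMH) test: "The primary outcome refers to a combined event in any of the twin and will be analysed for all pregnancies with available primary endpoint". The same section says "For the primary endpoint we expect to have a drop out rate of up to 25" per cent, because of the 3-year follow-up, but "we do not expect to have lost data for the secondary endpoints".

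Section 9.2 is built on the evaluable number: "To reach a power of at least 80%, we have to evaluate at least 500 patients", 250 per arm, raised to 672 for 25% loss.

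Section 9.4 reads: "The analysis will include all the subjects that have been randomised". The synopsis describes the trial as "in parallel groups, based on intention to treat comparing the placement of a cervical pessary with usual management", and section 4.2 says much the same.

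Under section 4.9 the study ends with the 3-year examination, "which will be conducted on the surviving children of the participating patients".

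No section of the supplied document states a missing-data assumption, an imputation method, a best/worst-case or tipping-point analysis, or a comparison of lost with retained pregnancies.

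**The concern.** The primary outcome combines death and disability in either twin. A fetal or neonatal death can be known years before the 3-year visit, and it settles the pregnancy as an event. An event-free result requires both children to be assessed at 3 years. Event pregnancies can therefore be more likely to have an available endpoint than event-free ones, and an available-case analysis overstates the event rate in each arm.

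The treatment comparison is biased when that overstatement differs between arms. This happens if loss differs by arm, which is plausible in an open-label trial with a parent-completed questionnaire. It also happens with equal loss if deaths are a larger share of events in one arm. Section 2.1 reports a six-fold fall in perinatal mortality with the pessary in the short-cervix subgroup of the earlier twin trial, so unequal death shares are not far-fetched.

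Section 9.1 also leaves unscored a pregnancy with one event-free twin and one unassessed twin.

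**Working it through.** **1. The plan's own figures.** Section 9.2 gives a pessary event rate of 8% and an odds ratio (OR) of 2.29. The control odds are 0.08/0.92 × 2.29 = 0.1991, a rate of 16.6%. The CMH sample-size formula with three equal strata gives 455 in total, or 500.4 with continuity correction, which matches 500. Rounding up to 84 per arm per stratum, 84/0.75 = 112 and 112 × 6 = 672. Both figures reproduce, and they show that 9.1 is the operative rule: 672 × 0.75 = 504 pregnancies tested, up to 168 not tested.

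**2. Model A: availability depends on outcome.** These are assumptions, as the documents give none of them: deaths are always known; pregnancies without a death are lost at random within arm at rate L; deaths account for a share s of events (10% to 75%).

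For true event rate p, per randomised pregnancy:
- observed events = ps + p(1 − s)(1 − L)
- observed non-events = (1 − p)(1 − L)
- observed odds = true odds × k, where k = 1 + sL/(1 − L)

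The available-case OR is therefore 2.29 × k(control)/k(pessary). Worked examples:
- Loss 20% pessary, 35% control, s = 75%: k = 1.1875 and 1.4038; OR = 2.29 × 1.182 = 2.71.
- Equal 25% loss, s = 25% pessary and 75% control: k = 1.0833 and 1.25; OR = 2.29 × 1.154 = 2.64.

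Simulation used 112 pregnancies per arm per stratum and the CMH test without continuity correction. The null case has 16.6% events in both arms. Simulated ORs sit slightly above the formula because of finite samples, and type I error varies between runs by a few tenths of a point.

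| Loss, pessary/control | Death share of events | Type I error | OR when true OR is 2.29: formula (simulated) |
|---|---|---|---|
| 25/25 | equal in both arms | 5.0% | 2.29 |
| 25/25 | 25% vs 50% | 6.1% | 2.47 (2.48) |
| 25/25 | 25% vs 75% | 9.7% | 2.64 (2.66) |
| 25/30 | equal, 10–75% | 5.0–5.8% | 2.31–2.42 |
| 20/30 | equal, 10–75% | 5.0–7.8% | 2.33–2.55 |
| 20/35 | equal, 10–75% | 5.1–11.9% | 2.35–2.71 (2.37–2.72) |
| 35/20 | equal, 10–75% | about as 20/35 | 2.23–1.94 (2.25–1.95) |

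In the last row power falls from 81% to 73% as the death share rises. With equal 25% loss and equal death shares it is about 85% to 90%.

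**3. Model B: a separate tipping-point illustration.** Here loss is taken as unrelated to outcome, so these figures should not be combined with Model A. Of 336 randomised per arm, 84 are missing and 252 observed. Expected observed events are 252 × 0.08 = 20.2 and 252 × 0.166 = 41.8, about 62 in all. For 20/252 vs 42/252, p = 0.003. Let missing controls have events at about 16.6%, that is 14 of 84, so the control total is 56/336:
- 18 events among the 84 missing pessary pregnancies: 38/336 vs 56/336, p = 0.046
- 19 events: 39/336 vs 56/336, p = 0.060

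Significance is lost at 19 of 84, or 23%, against the planned 8%.

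**The case against.** **Sections 9.1 and 9.4 need not conflict.** Section 5.3 uses intention to treat to mean continued follow-up after withdrawal or pessary removal. Section 9.4 can then mean analysis by allocated arm, with 9.1 naming the set for this endpoint. That reading is reasonable. A reader might infer that the plan abandons intention to treat or contradicts itself outright, but the documents do not support that. What remains is wording to reconcile.

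**Other planned analyses help.** The child-level random-effect models in 9.1 may keep an assessed twin whose co-twin is unassessed, and fetal/neonatal death is compared by arm with no loss expected. Both are useful, but neither addresses loss that depends on outcome.

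**Deaths may not always be known.** The neonatal-death endpoint in section 4.1.2 covers only the first 24 hours, so later deaths may go unrecorded in families lost to follow-up. This stands: it is an assumption of Model A, and the 11.9% figure also needs a 75% death share and a 20/35 gap. At 25/30 the error is at most 5.8%.

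**The result is fairly robust.** Missing pessary pregnancies would need an event rate nearly three times the planned one to overturn a result at design rates. This also stands, and it limits the severity. A reader might infer from 168 missing against 62 events that any positive result would be fragile, and the tipping point does not support that.

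**Conclusion.** The gap is real, and closing it is a cheap improvement. The plan expects up to 25% loss on the primary endpoint, tests available cases only, and includes nothing to show whether the result survives the missing data.

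Under Model A, type I error lies between 5.0% and 11.9%, and the design OR of 2.29 appears as about 1.95 to 2.72. The bias can go either way: towards the pessary if controls lose more, towards no effect if the pessary arm loses more. The size rests on assumed death shares and loss by arm. It also assumes that survivors are lost at random within arm; loss related to disability is not covered.

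Two further inferences should be resisted. Equal loss in both arms is not in itself reassuring; it leaves the test unbiased under Model A only when death shares are equal too. Nor do these figures forecast bias in favour of the pessary, because the documents give no loss by arm.

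**What to change.** 1. Keep the available-case CMH test as primary. State in 9.4 that women are analysed in the arm to which they were randomised, and that 9.1 names the primary analysis set.
2. State that a known death or disability in either twin is an event, and that one event-free twin plus one unassessed twin is missing, not event-free.
3. Pre-specify two sensitivity analyses on all randomised pregnancies:
   - multiple imputation by arm, using stratum, gestational age at birth, birth weight, neonatal morbidity, survival status and co-twin result, with the Mantel-Haenszel log odds ratio pooled by Rubin's rules;
   - a delta or tipping-point analysis, because imputation assumes that loss is unrelated to disability given those data.
4. Report endpoint availability by arm, since rule 2 itself makes availability depend on outcome.

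Section 9.1 expects complete secondary endpoints, so the birth and neonatal predictors should exist for all 672 pregnancies. No performance figure is claimed for this imputation model.

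The cost is a wording amendment (submitted under section 12 if judged substantial), a little extra analysis and some reliance on an imputation model. It needs no extra patients, visits or data items. It should be settled before any 3-year outcome by arm is seen.

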In a prospective randomised trial the "ProTwin Trial"⁸ 813 women with twin pregnancies at a gestational age of 16 weeks to 20 weeks were randomised to either

pessary treatment or expectant management. Subgroup analysis of women with a shortened cervix below the 25 percentile (=38 mm) showed for the pessary group a significant 6-fold decrease in perinatal mortality and a reduction of severe morbidity. This demonstrates that an early screening followed by an early intervention is essential for patients at-risk. A secondary analysis “*per protocol*” of the ProTwinTrial revealed that the success of pessary treatment was mostly dependent on the correct placement and the duration of the therapy ⁹.

A further prospective-randomised trial by Goya et. al ¹⁰ also proved a significant reduction of the preterm delivery rate in twin pregnancies with cervical shortening (<25 mm, 20-24 weeks of gestation) after placement of a pessary compared to expectant management; the reduction in mortality was less pronounced than in the ProTwin Trial. A new case-control-trial by Fox et al. ¹¹ showed a decrease in early preterm birth before 32 weeks of gestation (4.8% vs. 28.6%, P=.05), a considerable prolongation of pregnancy (65.2 d. vs. 52.1 d, P=.025) and a reduced neonatal morbidity (9.5% vs. 34.9%, P=.04) in twin pregnancies after pessary therapy.

A secondary analysis of the ProTwin Trial indicated a higher survival rate without neurodevelopmental disability in the long-term outcome 3 years after pessary treatment (92.4 vs. 73.8%, p=0.006) compared to expectant management ¹².

A prospective, randomised controlled trial by Nikolaides ¹³ and a cohort study by Monfrance ¹⁴ in twin pregnancies with short cervix showed no significant effect of the pessary therapy compared to expectant management.

Up to now there is just one Cochrane review available concerning pessary therapy and the authors concluded that in spite of the positive effects seen that more trials should be conducted ¹⁵.

2.2. Description of the study population.

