Women attending the reference hospital due to cervical shortening in twin pregnancies and fulfil the entry criteria (dichorionic twin pregnancy with cervical shortening \leq 25th percentile and do not fulfil the exclusion criteria), the study will be proposed. The patients will be informed of the intended therapeutic effect and possible side effects. If they agree and after obtaining their informed consent, they will be randomised according to the respective gestational week to either usual management (=control group) or cervical pessary placement up to 37 weeks (=pessary group). According to the gestational week and when the cervical shortening is under the 25th percentile the patients will be randomized to the following subgroups: gestational age in weeks 16-20, gestational age in weeks 20-24 and gestational age in weeks 24-28.

Specifically, the 25th centile of cervical length is defined at 32 mm, 30 mm and 28 mm for the 16+0 – 19+6, 20+0 – 23+6 and 24+0 – 28+0 weeks of gestation respectively.

2.3. Name and description of the device under investigation.

The Arabin cervical pessary, which is CE-certified for preventing SPB (CE 0482 / EN ISO 13485: 2012 + AC:2012 annex III of the council directive 93/42 EEC).

See annex I.

2.4. Statement that testing will be performed according to protocol, GCP and applicable legal requirements.

The Clinical Trial will be conducted following the protocol, the GCP, and all legal requirements.

3. Objective

This study aims to investigate the benefit of placing a cervical pessary in comparison to the expectant standard management in dichorionic twin pregnancies with cervical shortening \leq 25 percentile in terms of long-term survival without neurodevelopmental disability of the children.

Hereby, a standardized validated test called 'Ages and Stages 3rd edition' should evaluate the children's neurodevelopment at the age of 3 years. The test can be conducted by the parents and takes approximately 12 minutes. The questionnaires will be provided by the sponsor.

4. Design

4.1. Specific description of primary and secondary variables.

4.1.1. Primary outcome:

- Children`s survival without neurodevelopmental disability at the age of 3.

4.1.2. Secondary outcomes:

[figure not shown]
- Offspring
 - Time to birth
 - Preterm birth before 37 weeks: rate of delivery before 36+6 weeks
 - Preterm birth before 34 weeks: rate of delivery before 33+6 weeks
 - Preterm birth before 32 weeks: rate of delivery before 31+6 weeks

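### The pregnancy-level primary endpoint contradicts itself: a favourable outcome counted in any twin (9.1) is given an adverse 8% rate and an odds ratio without direction (9.2); the stated power is not in error

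*Combined protocol and SAP*

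**What the plan says.** The primary outcome is named as a good result throughout. Section 4.1.1 has "Children`s survival without neurodevelopmental disability at the age of 3", and the synopsis, the opening of 9.1 and the table of tests at the end of 9.1 agree with it in substance.

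Section 9.1 sets the unit and the counting rule: "The primary outcome refers to a combined event in any of the twin". The analysis is per pregnancy, by a "two-sided Cochran-Mantel-Haenszel-Test and a significance level of" 0.05, stratified by three gestation groups. The sentence does not say whether the event is the good result or its opposite.

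Section 9.2 gives the planning figures. For the pessary group, "we assume a combined event rate of at least 8% for the primary outcome". Then, "for the comparison of the pessary group with the control group we assume an odds ratio of 2.29". The synopsis traces this odds ratio to the "lower limit of a one-sided 90% confidence interval of the results" of the 3-year follow-up of the earlier twin pessary trial. For that follow-up, section 2.1 quotes disability-free survival, pessary against expectant management, as "92.4 vs. 73.8%, p=0.006".

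**The concern.** Joined to the outcome as named, the counting rule in 9.1 means that at least one twin is alive and unimpaired. A pair with one dead and one healthy twin would then be a success. The figures in 9.2 point the other way. A rate of 8% cannot describe disability-free survival when the cited rate is 92.4%, but it is close to the complement, 100 − 92.4 = 7.6%. The odds ratio does not resolve the conflict, because neither the event nor the numerator group is stated.

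The two readings disagree on every pair with exactly one affected twin. No other sentence in the protocol defines the endpoint at pregnancy level. The trial is open-label, and 9.1 schedules the secondary analyses right after the last delivery, 3 years before the primary one. If the wording stays as it is, the meaning of the endpoint could be settled after results by arm are known.

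**Working it through.** **Inputs from the documents.** Pessary rate 8%, odds ratio 2.29, 250 per group, three equal strata, two-sided 5% (synopsis, 9.1, 9.2); source rates 92.4% and 73.8% (2.1). **Assumed.** The within-pair correlation ρ is not given and is varied from 0 to 1. The 8% is taken as a pregnancy-level rate; the documents do not state its unit.

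**1. The plan's own figure.** Take 8% as the adverse rate under pessary, with the control odds 2.29 times higher:

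- Control odds = (0.08/0.92) × 2.29 = 0.0870 × 2.29 = 0.199, so the control rate is 0.199/1.199 = 16.6%.
- Mean rate = 12.3%. With 500 pregnancies in equal groups, the expected Cochran-Mantel-Haenszel deviation is 0.0861 × 500/4 = 10.76.
- Null variance = 125 × 0.123 × 0.877 = 13.49 (SD 3.672). Variance under the alternative = 125 × (0.0736 + 0.1385)/2 = 13.26 (SD 3.641).
- Power without continuity correction = Φ[(10.76 − 1.96 × 3.672)/3.641] = Φ(0.978) = 83.6%.
- With the correction, 0.5 is subtracted from 10.76: Φ(0.840) = 80.0%.

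Simulation of the stratified test gives 84.4% and 80.9%. Recruitment also follows: 84 per arm and stratum / 0.75 = 112, and 112 × 6 = 672. The plan's figures therefore belong to an adverse event in at least one twin.

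**2. The same event stated as its complement.** Both twins alive without disability: 92% v 83.4%. Odds ratio, pessary over control = (0.92/0.08)/(0.834/0.166) = 11.5/5.02 = 2.29. Power is identical, so swapping the label and the direction together costs nothing.

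**3. The literal 9.1 reading.** A pregnancy fails only if both twins are affected. Let q be the rate per child. The both-affected rate is b = q² + ρq(1 − q) and the any-affected rate is 2q − b. Solve 2q − b = 8% and 16.6%, then compute power on b with 250 per group. Example at ρ = 0.3: q = 4.8% and 10.2%, so b = 1.6% and 3.8%. The fourth column is the share of affected pregnancies with exactly one affected twin, (any − both)/any.

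| ρ (assumed) | Both affected, pessary | Both affected, control | One twin only, pessary / control | Power, uncorrected | Power, corrected |
|---|---|---|---|---|---|
| 0 | 0.17% | 0.75% | 98% / 95% | 16% | 5% |
| 0.1 | 0.60% | 1.66% | 93% / 90% | 20% | 10% |
| 0.3 | 1.60% | 3.79% | 80% / 77% | 33% | 23% |
| 0.5 | 2.86% | 6.42% | 64% / 61% | 47% | 39% |
| 0.8 | 5.48% | 11.74% | 31% / 29% | 70% | 65% |
| 1 | 8.00% | 16.61% | 0% / 0% | 84% | 80% |

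The normal approximation flatters the first row, where events are very few: simulation of the uncorrected test gives 8% there. From ρ = 0.1 upward, simulation agrees within about 2 points.

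**4. If 8% and 16.6% were child-level rates.** Any twin affected: power 98% at ρ = 0, 94% at 0.5 and 84% at 1. At least one healthy twin: 45%, 65% and 84%.

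**The case against.** The strongest reply is that the intended event can be recovered. The term combined event suits death or disability better than survival, 9.2 attaches the 8% to that term, the 8% matches the 7.6% complement of the cited rate, and the stated power reproduces on this basis. Section 9.1 also plans random-effects models for single children, so discordant pairs would be seen at child level as well. All of this stands. It shows what the sponsor most likely meant and that the sample size was computed coherently. It does not remove the contradiction: the outcome name with the counting rule says one thing and the planning rate says another, and the child-level models do not define the primary endpoint.

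Two stronger readings are tempting, and the documents support neither.

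- A reader might infer that the trial is underpowered, from the low values in the table. Those values hold only for the literal reading, only at low assumed correlations, and only if 8% and 16.6% are any-twin rates. The full span is 16% to 84%.
- A reader might apply 2.29 as pessary over control to the 8% event. That puts the control rate at (0.08/0.92)/2.29 = 0.0380 in odds, or 3.7%, with power 54% (47% corrected). This would mean planning for a harmful pessary. Section 9.2 names the two groups being compared but not whose odds are the numerator, and the rates in 2.1 run the other way.

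**Conclusion.** The endpoint is wrong as written; the power statement is not. The outcome name and counting rule in 9.1 contradict the 8% in 9.2, and the odds ratio carries no event or direction. For the adverse event in at least one twin, 250 per group gives 80.0% (corrected) or 83.6% (uncorrected), as the plan claims.

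What is at stake is the classification of pairs with exactly one affected twin. If 8% and 16.6% are any-twin rates, such pairs are most of the affected pregnancies unless the twin correlation is roughly 0.65 or higher. The correlation and the unit of the 8% are assumptions. If the 8% is a child-level rate, the any-twin event has 84% to 98% power, so the stated 80% is not put in doubt that way either.

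**What to change.** In the synopsis, 4.1.1 and 9.1, write: *Primary event: death or neurodevelopmental disability by 3 years in at least one twin; the favourable outcome is both twins alive without disability.* The sponsor should state which deaths count, including whether fetal deaths do. Section 4.1.1 is silent on this, and fetal death appears only among the secondary outcomes. Since 9.1 analyses pregnancies with an available endpoint, the definition should also say how a pair is classed when only one twin's 3-year result is known.

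In 9.2, write: *event rate 8% in the pessary group and 16.6% in the control group (odds ratio control versus pessary 2.29).*

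The cost is a few sentences and the sponsor's decision on those two rules, to be settled before outcome data by arm are examined. Sample size, test and stated power do not change.
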